#### *US Examination Protocol.*

A baseline ultrasound grayscale (US) scan of the treated lesion will be obtained and the following criteria assessed: the size, shape, and orientation of the site; echogenicity compared to surrounding tissue. Standard PDI of the LABC will also be performed. The distribution of color

signals and the overall color content of mass will be evaluated by comparing the pattern and amount of color to the normal surrounding breast. If uniform, the color will be categorized as less intense, iso-intense or more intense than normal breast. If non-uniform, the color will be described by location, intensity and distribution. Irregularity of the course of the vessels will be scored on a scale from 1.0 to 5.0 (smooth to severe irregularity) and anastomoses between adjacent vessels will be noted (as 1-2, 3-5 or >5 vessels connecting). The vascular pattern will also be graded as peripheral, radial from one or multiple sites, spotty or a combination. Digital clips of the two baseline imaging modes will be acquired.

The contrast administration will be an intravenous infusion of 2 vials of Definity/50ml saline through the subjects' vascular port (established as part of their standard of care), with infusion rates of 4 to 10 ml/min (titrated to effect). Next, we will run a power optimization algorithm to establish the individualized acoustic parameter settings for the case (on the first imaging study only). We will use those parameters for all subsequent imaging studies to sweep the area of the LABC to acquire 3D, pulse inversion SHI grayscale volume data. The digital clips and RF data obtained from each 3D SHI injection will be transferred to a PC for off-line analysis. The SHI images will be qualitatively analyzed as described above. This protocol will be followed for all the contrast studies for each subject (except for the power optimization algorithm, which will only be run once for each patient). All subjects will be closely monitored by a physician during and following the study.

#### *Data Assessments.*

The pre- and then post-contrast US imaging will be evaluated for each patient at all 4 time points in one reading as follows: grayscale, grayscale and PDI (baseline), and grayscale and 3D SHI. While this may introduced some bias from pre- to post-contrast results, we considered this the

more realistic approach to how US contrast may be used in clinical practice. Each case will be read independently by the 2 experienced co-investigators (more than 15 years of expertise in breast imaging) blinded to the contrast-enhanced MRI evaluations, to allow repeatability to be assessed. All US studies will be rated on a quasi-continuous scale from 0 to 100 ranging from “no change relative to pre-therapy” over “indeterminate” to “definite changes seen.” Using a quasi-continuous 100-point rating scale has an intuitive probabilistic interpretation and is known to improve the assessment of the capabilities of the imaging modes studied.

Moreover, the 3D SHAPE results (i.e., IFP estimates) will be compared to lesion size, tumor response, DFS and overall survival. Results will also be compared to MRI enhancement kinetics and imaging measurements of lesion size obtained before and after completion of the chemotherapy. Once surgery has been performed the following variables estrogen, progesterone and HER2 receptor presence or absences; presence or absence of hemorrhagic, necrotic, or other component of the lesion (and their location if present); histological margins; lesion size; TNM staging; histological lesion type; presence or absence of vascular invasion; histological and cytological grade; presence or absence of metastases; node staging; and percentage of the lesion that was invasive or *in situ* will be collected as part of the patient’s clinical care and correlated with the imaging results. Finally, the ability of 3D SHI to image angiogenesis (specifically fractional tumor vascularity) will be compared to specimens stained for an immunohistochemical predictor of angiogenesis, specifically a monoclonal antibody against the PECAM endothelial cell marker (anti-CD31; Dako Corporation, Carpinteria, CA). The PI has developed the necessary software for quantitative analysis of contrast enhanced US images and specimens

stained with CD31 using a histomorphometry system based on an SMZ-10A microscope (Nikon, Melville, NY) and ImagePro Plus software.

*Statistical Analysis.* Our statistical analysis will address the primary objective of this study by answering two major questions:

1. Can *in vivo* 3D SHAPE monitor the effect of neoadjuvant chemotherapy on breast cancer IFP?
2. Can *in vivo* 3D SHI monitor the effect of neoadjuvant chemotherapy (i.e., responders/non-responders) on breast cancer?

The findings of SHI/SHAPE will be correlated to vascular morphology (i.e., tumor angiogenesis ascertained with CD31) and other pathological findings; including size, vascularity, presence or absence of receptors. For the pre and post-contrast enhanced comparisons, dichotomous parameters (e.g., responder/non-responder) and ranked data (less, iso, or more intense) will be analyzed with the McNemar test which measures significance of changes in related samples (pairwise comparisons) for each time point. For variables in which accurate numerical measurement is possible (e.g., IFP and vascularity), the techniques will be compared using repeated measures logistical regression and ANOVA.

To answer statistical question 2, the ability of the imaging tests to distinguish responders from non-responders will be compared using ROC analysis, while the incremental validity of combining imaging assessments will be analyzed using logistic regression and ROC analyses. The tests are fundamental grayscale US imaging, PDI, 3D SHI and contrast

enhanced MRI, while patient outcomes and pathology will provide the reference standards. A power analysis was performed using PASS 12 (NCSS, East Kaysville, UT) to estimate the number of cases required to produce clinically acceptable results. A sample size of 20 responders and 20 non-responders (i.e., approximately halfway between 20 and 50 subjects) achieve 80% power to detect a difference of 0.174 between a diagnostic test with an area under the ROC curve ( $A_z$ ) of 0.800 (the null hypothesis) and an actual  $A_z$  of 0.974 using a one sample, two-sided z-test with a significance level of 0.05. The ratio of the standard deviation of the responses in the two groups was assumed to be 1.00. All analyses will be performed with Stata 12.0 (Stata Corp., College Station, TX).

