## **1. Introduction**

Systemic preoperative therapy (neoadjuvant chemotherapy alone or in combination with endocrine therapy) is widely used in the treatment of locally advanced, primary breast cancer (LABC) and is considered the standard of care for these patients. Some 20 % of all primary breast cancers are diagnosed as LABC or are carcinomas with an unfavorable tumor-to-breast size ratio. In the largest study to date (>1500 patients), there was no statistical differences

between survival among patients that underwent neoadjuvant therapy (69%) and patients receiving adjuvant therapy (70%;  $p=0.80$ ) after 9 years. Likewise, for disease free survival (DFS), which was 53 and 55 %, respectively, in the adjuvant and the neoadjuvant groups ( $p=0.5$ ). These results were supported by a recent meta-analysis involving almost 4000 women, which found no statistical or clinical differences between neoadjuvant and adjuvant therapy arms associated with survival or disease progression and this result was recently confirmed even after 10 years of follow-up. Moreover, neoadjuvant therapy is increasingly being used to treat operable, palpable breast cancers as well, in an attempt to avoid mastectomies and allow for breast conserving surgery instead. Neoadjuvant therapies have the potential to improve survival and reduce morbidity by downstaging tumors, since a reduction in the primary tumor volume can be used to predict a reduction in micrometastatic tumor volume and clinical benefit. However, monitoring the *in vivo* response to therapy is essential to distinguish between patient responders and non-responders as early as possible to allow for better, individualization of treatment options. A noninvasive technique that reliably determines breast cancer response to therapy may improve treatment outcomes.

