the pathological reference standard). For the US techniques where data from multiple time points are available, this analysis will be repeated for each time point. All of the statistical analyses proposed for the human clinical trial will be repeated split by racial and ethnic groups to determine if clinically important race/ethnicity differences exist in the ability of 3D SHI/SHAPE to monitor breast cancer treatment.

Finally, the vascularity measures obtained from the CD31 stained breast tumor specimens will be compared to the fractional tumor neovascularity data to determine if any correlation exists (in baseline PDI or contrast enhanced mode). The existence of a linear relationship between US and pathologic data will be assessed using single variable linear regression techniques and reverse stepwise multiple linear regression analysis.

All analyses and computations will be performed using Stata 12.0 (Stata Corporation, College Station, TX), while the study database will be designed and implemented in Filemaker Pro 10.0 (Filemaker Inc, Santa Clara, CA). This database will contain all patient information (except names and other identifiers) and the results of the various US imaging modes as well as the pathology results.

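### The reading rules let early scans be rated with the final scan in view, and do not state that readers are blinded to the reference standards

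*Combined protocol and SAP*

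**What the plan says.** Each woman has four contrast studies: before chemotherapy, at about 10% and 60% of it, and after its completion (section 4, Patient Enrollment). Under Data Assessments, ultrasound "imaging will be evaluated for each patient at all 4 time points in one reading". The same sentence then lists the modes to be read: grayscale alone, grayscale with PDI, and grayscale with 3D SHI. The plan concedes that "this may introduced some bias from pre- to post-contrast results", and accepts this as closer to how contrast ultrasound would be used in practice.

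On the readers: "Each case will be read independently by the 2 experienced co-investigators", who are "blinded to the contrast-enhanced MRI evaluations, to allow repeatability to be assessed". Every ultrasound study is scored from 0 to 100, and the low end of the scale means "no change relative to pre-therapy". Section 5.4 on blinding concerns the trial drug only.

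The ROC analysis takes patient outcomes and pathology as reference standards (section 4, Statistical Analysis; section 7.2.2). Section 4 applies the McNemar test at each time point. Section 7.2.2 says of the Cox analysis that "this analysis will be repeated for each time point". The Introduction gives the clinical purpose of monitoring: to "distinguish between patient responders and non-responders as early as possible".

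**The concern.** An early rating is useful only if it reflects what could be seen early. If all four scans are opened in one sitting, with no set order and nothing locked, an indeterminate picture at 10% of treatment can be pulled towards a known ending. The rating then measures partly the final scan, and no later analysis can recover the uncontaminated score.

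The plan's reason for reading modes together does not extend to this. Reading grayscale, then PDI, then SHI in one session resembles practice. Reading the 10% scan beside the end-of-treatment scan does not, because a clinician at 10% of treatment does not have that later scan.

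The blinding has a related gap. Readers are shielded from a comparator test, MRI, but nothing shields them from the standards against which all the tests are judged. Clips are stored for off-line analysis and no reading date is given, so the plan does not exclude reading after surgery.

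At stake are the per-time-point McNemar and Cox results where they use reader judgements, and any ROC analysis of the early scans.

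**Working it through.** **1. What the text rules out**

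| Safeguard | Stated in the plan? |
|---|---|
| Blinding to MRI | Yes (Data Assessments) |
| Two readers independent of each other | Yes (Data Assessments) |
| Order of modes | Yes, pre- then post-contrast; bias admitted and justified |
| Order of time points | No |
| Locking a time point's ratings before a later scan is seen | No |
| Blinding to pathology, clinical response or outcome | No |
| Date of reading relative to surgery | No |

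**2. The plan's own figure**

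The Statistical Analysis text claims 80% power for Az 0.800 against 0.974 with 20 responders and 20 non-responders (one-sample z-test, two-sided 0.05, SD ratio 1.00). I used the binormal rating-data variance

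V = 0.0099·exp(-a²/2)·[(5a²+8)/n₁ + (a²+8)/n₂], with a = 1.414·Φ⁻¹(Az).

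The standard errors are 0.0773 at Az 0.800 and 0.0264 at 0.974. Power = Φ[(0.174 - 1.96×0.0773)/0.0264] = 0.803. The figure reproduces. This point does not dispute it, and changing the reading rules would not change the sample size.

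**3. How carry-over would act (illustration)**

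Assumptions not in the documents: true early Az 0.70; final-scan Az 0.90; unit-variance binormal errors with correlation ρ of 0 or 0.5. The reader gives weight w to the final scan and 1-w to the early one. Then

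Apparent Az = Φ{[(1-w)·Φ⁻¹(0.70) + w·Φ⁻¹(0.90)] / √[(1-w)² + w² + 2w(1-w)ρ]}.

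With Φ⁻¹(0.70) = 0.5244, Φ⁻¹(0.90) = 1.2816 and w = 0.25:

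- Numerator: 0.75×0.5244 + 0.25×1.2816 = 0.7137.
- ρ = 0: denominator √0.625 = 0.7906, apparent Az 0.817.
- ρ = 0.5: denominator √0.8125 = 0.9014, apparent Az 0.786.

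| Weight on final scan | Apparent early Az, ρ = 0.5 | ρ = 0 |
|---|---|---|
| 0 | 0.700 | 0.700 |
| 0.10 | 0.735 | 0.746 |
| 0.25 | 0.786 | 0.817 |
| 0.50 | 0.851 | 0.899 |

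Part of the rise comes from averaging two scans with partly independent errors. If the final scan were no better than the early one (Az 0.70), w = 0.25 would still give Φ(0.5244/0.9014) = 0.720 at ρ = 0.5 and Φ(0.5244/0.7906) = 0.746 at ρ = 0. That gain is also unavailable to someone who has only the early scan, but it shows how far the upper figures depend on low correlation.

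**4. Against the plan's null of 0.80 (illustration)**

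Assume a true early Az of exactly 0.80, final-scan Az 0.90 to 0.95, ρ 0.3 to 0.6, and 20 + 20 subjects. With the variance in step 2, the upper rejection limit is 0.80 + 1.96×0.0773 = 0.9515.

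| Weight on final scan | Apparent Az | Chance of rejecting Az = 0.80 |
|---|---|---|
| 0 | 0.80 | 5% |
| 0.25 | 0.85-0.89 | 7-15% |
| 0.50 | 0.88-0.94 | 14-39% |

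**The case against.** The strongest objection is that the key sentence is ambiguous. The list that follows it names modes, not time points, and the bias then discussed is between modes. Both fit a reading in which all modes are viewed together separately at each of the four visits. A reader of the 10% scan would then not need to see the final one. This stands, and the point cannot assert that all four scans are read together. But neither meaning comes with an order of time points, a lock, or blinding to the reference standards.

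Four stronger readings are tempting and go beyond the documents:

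- **That readers know the pathology result, so every Az is inflated.** The plan is silent on what they know and on when they read. Only the absence of stated blinding is documented.
- **That a planned Az at 10% and 60% is biased.** The ROC text names no time point. The repetition in section 7.2.2 belongs to the Cox analysis, and the per-time-point wording in section 4 belongs to McNemar. An early-scan ROC is a natural analysis but not a specified one.
- **That all trial results are exposed.** The problem lies in the subjective grayscale, PDI and SHI ratings. SHAPE pressure estimates and fractional vascularity are quantitative and less exposed. Sight of the pre-therapy scan is no flaw either, because the scale requires it.
- **That modes should be read apart.** The plan discloses that choice and gives a reason.

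It is also fair to say that the sizes above are assumed throughout. They show direction and plausible scale, not an expected bias.

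**Conclusion.** The concern holds in limited form. The procedure as worded permits ratings of the 10% and 60% scans to be shaped by the end-of-treatment scan. It does not state that readers are kept from pathology and outcomes. The plan's stated justification covers neither.

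The size cannot be derived from the documents. On the assumptions in step 3, a 25% weight on the final scan moves an early Az of 0.70 to 0.79-0.82. A 10% weight gives about 0.74-0.75, and a 50% weight 0.85-0.90. If the sentence means separate readings at each visit, and those are done before later scans exist, the carry-over between time points disappears. The unstated blinding to the reference standards would remain. This is a cheap improvement to the method, not an error in the sample size or the choice of tests.

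**What to change.** Amend Data Assessments in section 4 to:

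- say whether the four time points are read in one session or separately, and when reading takes place relative to surgery;
- show scans in chronological order, with the pre-therapy scan available for comparison;
- require each time point's ratings to be entered and locked before the next time point is opened;
- blind readers to pathology, clinical response and outcome as well as MRI.

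Reading the modes together within a time point can stay as planned. The cost is a set of reading instructions, a locked form and slightly longer sessions. Clips are already stored for off-line analysis, so no extra subjects, scans or readers are needed.

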#### **7.2.2 Analysis of Results**

For the pre and post-contrast enhanced comparisons, dichotomous parameters (e.g., responder/non-responder) and ranked data (less, iso, or more intense) will be analyzed with the McNemar test which

measures significance of changes in related samples (pairwise comparisons). For variables in which accurate numerical measurement is possible (e.g., IFP and vascularity), the techniques will be compared using logistical regression and an ANOVA.

The ability of the imaging tests to distinguish responders from non-responders will be compared using ROC analysis, while the incremental validity of imaging assessments will be analyzed using logistic regression and ROC analyses. The tests are fundamental grayscale US imaging, PDI, 3D SHI and contrast enhanced MRI, while patient outcomes and pathology will provide the reference standards. All studies will be rated on a quasi-continuous scale from 0 to 100, since this has an intuitive probabilistic interpretation and improves the assessment of the characterization capabilities of the imaging modalities compared to using a coarser 6-point scale. Logistical regression techniques will be used to combine the 3 US imaging modes and MRI as well as to incorporate the quantitative parameters (i.e., SHAPE IFP estimates) into the US evaluation before repeating the ROC analysis. This will allow all possible combinations to be compared to one another (e.g., MRI versus all the US modes combined or MRI and grayscale US versus MRI and grayscale US and SHI, etc.). Differences between ROC curves will be tested by computing Mann-Whitney statistics.

All histopathological variables will be compared to imaging judgments of vascularity for the different modalities. When both sets of variables are nominal, chi-square tests will be conducted. When both types of variables are ordinal or continuous, correlations will be calculated. When one type of variable is nominal and one continuous non-parametric rank order tests such as Mann-Whitney U-tests or Kruskal-Wallis tests will be performed. Inter-observer variability will also be determined by calculating the intraclass correlation coefficient.

Comparisons of subject outcomes (i.e., responders vs. non-responders) established by monitoring the treatment with the different imaging modalities will be conducted with Cox Survival analysis (against

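### The 0–100 ultrasound reading scale rates certainty that something has changed, without direction, yet the ROC analysis uses it to separate responders from non-responders

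*Combined protocol and SAP*

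**What the plan says.** Data Assessments in Section 4 covers all four imaging time points and has two readers independently rate all ultrasound studies on a "scale from 0 to 100 ranging from “no change relative to pre-therapy” over “indeterminate” to “definite changes seen".

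The Statistical Analysis part of Section 4 poses two questions for the primary objective. For the second, "the ability of the imaging tests to distinguish responders from non-responders will be compared using ROC analysis", "while patient outcomes and pathology will provide the reference standards". The tests are grayscale ultrasound, power Doppler, 3D SHI and contrast-enhanced MRI.

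Section 7.2.2 repeats the scale in the paragraph that sets out the ROC analysis: "All studies will be rated on a quasi-continuous scale from 0 to 100, since this has an intuitive probabilistic interpretation". It gives no anchors there, for ultrasound or for MRI.

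The only power calculation in the plan is for an ROC area: "A sample size of 20 responders and 20 non-responders" are said to "achieve 80% power to detect a difference of 0.174", from an Az "of 0.800 (the null hypothesis) and an actual" Az "of 0.974 using a one sample, two-sided z-test".

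**The concern.** ROC analysis ranks patients by score, so the score has to rise with the likelihood of response. The anchors here describe how sure the reader is that a change since pre-therapy is present. They say nothing about its direction. A tumour that has plainly grown, or plainly become more vascular, satisfies the top anchor as well as one that has plainly shrunk. The first patient is a non-responder and the second may be a responder, yet both can sit near 100. The probabilistic interpretation that the plan claims for the scale then concerns the probability of change, not of response.

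At stake are the single-modality ultrasound ROC curves that answer the second primary question, and any comparison built on them. There is also a smaller wording gap: the scale is relative to pre-therapy but applies to all ultrasound studies, including the pre-therapy scan, where it carries no information.

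**Working it through.** **1. Does any other text supply the direction?**
- The US Examination Protocol grades colour as less, iso- or more intense. That is relative to normal breast, not to the pre-therapy scan, and the plan analyses it with the McNemar test.
- Section 7.2.2 adds the SHAPE pressure estimate by logistic regression before repeating the ROC analysis. That may restore some direction in combined models, but not in the curves for grayscale, power Doppler or 3D SHI alone.
- Nothing tells readers to count only favourable change, and nothing recodes the score before the ROC analysis.

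**2. Reproduce the plan's power figure.** Inputs from Statistical Analysis, Section 4: n = 20 per group, Az 0.800 (null) and 0.974 (alternative), two-sided 0.05, SD ratio 1.00. The rating-scale binormal approximation for equal groups is

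V(A) = 0.0099 × exp(−a²/2) × [(5a² + 8) + (a² + 8)], with a = 1.414 × Φ⁻¹(A) and SE = √(V/20).

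- A = 0.800: a = 1.190, V = 0.1195, SE = 0.0773.
- A = 0.974: a = 2.748, V = 0.0139, SE = 0.0264.
- Power = Φ[(0.174 − 1.96 × 0.0773)/0.0264] = Φ(0.85) = 80.3%.

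The stated 80% is reproduced. It presumes a score that orders responders above non-responders.

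**3. Effect of progressing non-responders.** Let p be the share of non-responders who progress, and c the probability that a responder outscores a progressor. Then

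Az = (1 − p) × 0.974 + p × c.

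If progressors score exactly like responders, c = 0.5. A value of c = 0.75 illustrates partial overlap. Both p and c are assumptions, since the documents give neither. The power column puts the c = 0.5 Az into the formula of step 2.

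| p (of 20 non-responders) | Az, c = 0.5 | Az, c = 0.75 | Power, c = 0.5 |
|---|---|---|---|
| 0 | 0.974 | 0.974 | 80% |
| 5% (1) | 0.950 | 0.963 | 49% |
| 10% (2) | 0.927 | 0.952 | 31% |
| 20% (4) | 0.879 | 0.929 | 13% |
| 30% (6) | 0.832 | 0.907 | 5% |

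Example: 0.9 × 0.974 + 0.1 × 0.5 = 0.8766 + 0.05 = 0.927. With c = 0.5, Az reaches the null value at p = 0.174/0.474 = 36.7%, about 7 of 20.

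The power level depends on the standard error used, but the fall does not. In a simulation with c = 0.5 and a DeLong standard error, power was 99%, 94%, 76% and 29% with 0, 1, 2 and 4 progressors.

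**4. Comparisons between modalities.** With a common p and c = 0.5, order is preserved and differences shrink by the factor (1 − p). At p = 10%, true values of 0.974 and 0.90 become 0.927 and 0.860, so the gap goes from 0.074 to 0.067. Order can reverse only if modes differ in how they score progressors. For illustration, take 20% progressors. A mode with Az 0.974 that scores all of them as changed falls to 0.879. A mode with Az 0.90 that misses progression, and scores these patients like other non-responders, stays at 0.900. The documents do not say whether such a difference exists.

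**The case against.** The strongest defence is context. Statistical Analysis in Section 4 equates the effect of chemotherapy with responder status. Two readers with more than 15 years of breast-imaging experience, seeing all four time points together, could well take change to mean treatment effect. If so, progressors would be scored low and nothing would be lost. This is plausible but unwritten, and two independent readers could settle it differently. It makes the harm possible rather than certain. It does not remove the gap.

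A reader might also infer more than the text supports:

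- **That the scale measures how much the tumour changed.** Its anchors run through indeterminate to definite, so it rates certainty that change is present.
- **That Az is biased downward for every modality.** The loss is zero without progressors and smaller with partial overlap. For MRI the anchors are not stated at all, so a bias there would be assumed.
- **That comparisons between modalities are invalid.** With a common p, step 4 shows shrinkage without a change of order. Distortion needs unequal detection of progression, which the documents neither show nor exclude.
- **That the pre-therapy rating adds bias.** No text says that baseline ratings enter the ROC analysis, so this is a matter of wording.

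The scope is also limited. The first primary question rests on the SHAPE pressure estimate, a signed measurement. Fractional vascularity and lesion size do not use the reading score either.

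**Conclusion.** The concern holds in a conditional form. As written, the anchors allow a clearly progressing non-responder to rank with responders in the reader-scored ROC analysis, the type of analysis for which the plan gives its only power calculation. No other text corrects this for the single-modality ultrasound curves.

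The possible loss runs from nothing at p = 0 to 0.047 in Az at 10% and 0.142 at 30% (0.974 − 0.927 and 0.974 − 0.832). It rests on three assumptions: that readers follow the anchors literally, that some non-responders progress, and that progressors score exactly like responders. The documents support no particular value of p. With only 20 planned non-responders, one or two such patients would already matter. The 80% power statement is correct for its own inputs, and the signed measures stand.

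**What to change.** Before reading begins, change the reading form, Data Assessments in Section 4, and Section 7.2.2 as follows:

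- Re-anchor the scale as confidence in response: 0 = definite non-response, whether stable or progressing; 50 = indeterminate; 100 = definite response.
- Apply it only to the three ultrasound studies after treatment starts, with the pre-therapy study as reference.
- State the same anchors for the MRI rating.
- If certainty of any change is still of interest, record it as a separate descriptive item outside the ROC analysis.

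The cost is a few lines of text and a revised form. Cases already read would need re-scoring, because direction cannot be recovered from the existing score alone. The sample-size calculation need not change.

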## **3. Specific Aims for the Human Clinical Trial.**

- 1) To evaluate the ability of 3D SHI and SHAPE to track changes in LABC angiogenesis and IFP, respectively, by studying women undergoing neoadjuvant chemotherapy before as well as with around 10% and 60% of the neoadjuvant chemotherapy treatment delivered and after

completion of the neoadjuvant chemotherapy treatment and comparing results to MRI and pathology.

- 2) Finally, as a secondary aim, to compare the 3D SHI depiction of breast cancer angiogenesis in humans to CD31, an immunohistochemical predictor of angiogenesis.

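### Receptors, histological type and grade are collected after surgery with no pre-treatment source named, and the CD31 comparison states neither its tissue source nor which of the four scans it is paired with

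*Combined protocol and SAP*

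**What the plan says.** Section 4, Data Assessments, opens its pathology list with "Once surgery has been performed the following variables estrogen, progesterone and HER2 receptor presence or absences". The same list contains "histological lesion type; presence or absence of vascular invasion; histological and cytological grade". The variables come from "clinical care and correlated with the imaging results", with no scan named. The Synopsis repeats the list with the same timing. Every subject has neoadjuvant chemotherapy, so surgery follows treatment.

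Section 3 gives the single secondary aim: "to compare the 3D SHI depiction of breast cancer angiogenesis in humans to CD31, an immunohistochemical predictor of angiogenesis". On the tissue, Data Assessments says that fractional tumour vascularity on 3D SHI "will be compared to specimens stained for an immunohistochemical predictor of angiogenesis". The Statistical Analysis part of section 4 says "The findings of SHI/SHAPE will be correlated to vascular morphology (i.e., tumor angiogenesis ascertained with CD31) and other pathological findings"; receptor status is named among those findings. Section 7.2.2 says "the vascularity measures obtained from the CD31 stained breast tumor specimens will be compared to the fractional tumor neovascularity data".

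Patient Enrollment (section 4) plans four contrast studies per subject: before chemotherapy, at about 10% and 60% of it, and after completion.

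**The concern.** Receptors, type and grade have to be read in tumour. A patient whose tumour has gone has none left in the surgical specimen, so the value is lost because of the outcome the trial studies. In the remaining patients the value describes tumour that has survived chemotherapy, yet nothing stops it being correlated with a scan taken before or early in treatment. Any association between these features and the imaging would then be estimated in a group selected by response.

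For CD31 the difficulty is an undefined comparison. The primary aim is to track changes in angiogenesis across the four scans. On that premise, a scan and a specimen from different points in treatment need not show the same vascularity. Unless the tissue and scan are fixed in advance, a weak correlation could mean that SHI measures vascularity poorly or only that the vessels changed in between. A strong one could be the best of several pairings.

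**Working it through.** **1. The plan's own power figure.** The only power statement is 80% for an AUC of 0.800 against 0.974 with 20 responders and 20 non-responders (section 4, Statistical Analysis). With the binormal rating-data variance, V = 0.0099·exp(−a²/2)·(5a² + 8 + (a² + 8)/R)/n, a = 1.414·z(AUC), R = 1 and n = 20, the standard errors are 0.0773 under the null and 0.0264 under the alternative. Power = Φ((0.174 − 1.96 × 0.0773)/0.0264) = 80.3%. The figure reproduces under this variance. It uses no pathology correlation or CD31 value, so this point does not affect it. No sample size or effect size is stated for CD31.

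**2. Receptors, type and grade.**
- Time of collection: after surgery (Synopsis; Data Assessments).
- Use: correlated with imaging, no time point given. Section 7.2.2 likewise compares all histopathological variables with imaging judgments of vascularity.
- Pre-treatment source: none named, although a breast cancer diagnosis is an entry criterion.
- Rule for a specimen without residual tumour: none.

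Size, by assumption: if 20% to 40% have no residual tumour, 0.20 × 40 = 8 to 0.40 × 40 = 16 lack these values (4 to 8 of 20; 10 to 20 of 50). If all of them count as responders (the plan does not define the term) and the split is the assumed 20/20, then 12 down to 4 responders keep a value, against all 20 non-responders.

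**3. CD31.**
- Tissue: called only specimens, or stained breast tumour specimens.
- Scan: 7.2.2 names an imaging mode, not a time point. Baseline there qualifies PDI and means unenhanced, as in Data Assessments; it does not mean pre-therapy.
- Per-time-point wording attaches to the McNemar comparisons (section 4) and the Cox analysis (7.2.2), not to CD31.

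If all four pairings were tested at 0.05, the chance of at least one false positive would be 1 − 0.95⁴ = 18.5% under independence.

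**4. Illustration of loss at the low end of CD31.** Assume bivariate normal data and that the patients lost are exactly those with the lowest CD31. For a lost fraction p, let α = z(p), λ = φ(α)/(1 − p) and v = 1 + αλ − λ². Then r′ = r√v / √(r²v + 1 − r²). For p = 0.20: α = −0.842, λ = 0.350, v = 0.583, and r = 0.60 gives r′ = 0.458/0.922 = 0.50. Power = Φ(atanh(r′)·√(n − 3) − 1.96).

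| Lost | r′ (true 0.60) | Power, 40 enrolled | Power, 20 enrolled |
|---|---|---|---|
| 0% | 0.60 | 99% (n = 40) | 82% (n = 20) |
| 20% | 0.50 | 84% (n = 32) | 50% (n = 16) |
| 30% | 0.47 | 71% (n = 28) | 39% (n = 14) |
| 40% | 0.44 | 58% (n = 24) | 29% (n = 12) |

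At the other extreme, loss unrelated to CD31 leaves r at 0.60. Power at 40% loss is then Φ(0.693 × √21 − 1.96) = Φ(1.22) = 89% with n = 24, and Φ(0.693 × √9 − 1.96) = Φ(0.12) = 55% with n = 12.

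**The case against.** The strongest reply is that much of this rests on silence.

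- A reader might infer that CD31 is measured only in surgical tissue. That is the natural reading, because the CD31 sentence follows the surgical list, but the documents do not state it.
- A reader might infer that the plan pairs CD31 with all four scans. No scan is included or excluded; the fault is an unspecified pairing, not a planned wrong one.
- A reader might conclude that complete responders have no CD31 value. The plan describes CD31 as an endothelial marker, and a resected tumour bed could still be stained. Whether that counts as a tumour specimen is left open.
- A reader might expect early scans to correlate weakly with surgical CD31 whatever SHI can do. If patients largely keep their vascularity ranking through treatment, that fails.
- Collection within clinical care does not forbid taking a biopsy result from the record.
- The aim is secondary and descriptive, in a first-in-humans study.

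These objections stand, and they limit the CD31 part to what is unspecified. They do not answer the receptor part, where the plan gives a collection time after chemotherapy and no alternative source. Nor do they supply the missing CD31 definition: if the tissue were diagnostic biopsy, the matching scan would be the pre-therapy one, and the plan does not say that either.

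**Conclusion.** The point holds in two parts. First, as written, receptors, type and grade are collected after chemotherapy. They will be unavailable where no tumour remains, with missingness determined by response, and will describe treated tissue elsewhere. Second, the secondary aim does not define its comparison, because neither CD31 tissue nor scan is stated. It should be corrected, but it reaches only the secondary aim and the pathology correlations.

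The size is uncertain. The 8 to 16 of 40 depends on an assumed 20% to 40% without residual tumour. The fall from 0.60 to between 0.50 and 0.44 is a worst case: it also assumes that patients without evaluable CD31 are exactly those with the lowest values, and a weaker link gives a smaller loss. The documents supply neither the rate nor the link. Treating the post-chemotherapy scan as the match for surgical tissue also assumes a short scan-to-surgery interval, which the plan does not give.

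**What to change.** 1. In Data Assessments and the Synopsis, add abstraction of ER, PR, HER2, histological type and grade, where reported, from the existing pre-treatment diagnostic pathology report. Use these values for correlations with pre-therapy and on-treatment imaging. Keep the surgical values as post-treatment findings.
2. In 7.2.2, state the CD31 tissue source. Make the time-matched scan the main secondary-aim comparison; for surgical tissue that is the post-chemotherapy scan. Label pairings with earlier scans exploratory. Define evaluable tissue, including whether a tumour bed without residual tumour qualifies, and limit the conclusion to patients who have it.

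Staining archived diagnostic tissue for CD31 and pairing it with the pre-therapy scan is optional.

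The cost is some record abstraction, a few sentences of analysis text, and fewer headline CD31 pairings. Item 1 removes the response-dependent gap wherever the diagnostic report holds the variable. Item 2 makes the CD31 result interpretable, but it does not remove the attenuation in the table; that remains a limitation to report.
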